## Introduction

The purpose of Aim 1 is to study the effect of a screening-based approach to delivery of the CRx-D intervention on caregiver self-efficacy [primary outcome] and more distal caregiver and PWD health and healthcare outcomes.

## **Measures Used**

## Caregiver Self-efficacy [Aim 1]

The primary outcome for Aim 1 will be assessed using the 4-item self-efficacy sub-domain from the 2015 Caregiver Dementia Care and Self-Efficacy Survey developed by Jennings et al for the NIAand CMS-funded Alzheimer's and Dementia Care Program. We selected this measure because it is, to our knowledge, the only available measure validated specifically for ADRD caregivers that assesses self-efficacy for accessing services. Per Jennings' protocol, responses to each of the 4 items in the self-efficacy domain will be scored from 1=strongly disagree to 5=strongly agree and averaged. We will also assess caregiver self-efficacy for self-care using our measure from the CRx-2 trial. This measure derives from Bandura's Self-Efficacy theory: "How confident are you in your ability to find resources in your community that help you manage your [your care recipient's] health?" (5-point Likert scale "not at all confident" to "completely confident").

### **Psychosocial Outcomes**

HRSNs will be assessed at baseline and follow-up using the CMS tool. The "core" tool includes 10 validated items to assess 5 needs domains: food, housing, interpersonal safety, transportation, and utility support. We will also include the domains "family and community support" (including social isolation) (2 items) and "financial strain" (1 item). Scoring will be per CMS instructions. For follow-up surveys after 1 week, we will assess needs occurring in the interval since the last interview and, when a need is identified, during the past 30 days. In addition to assessing unmet HRSNs, we will assess unmet caregiving-specific resource needs using a measure building on prior studies and our own qualitative work. Caregiver well-being will be assessed using PROMIS Neuro-QoL ShortForm v1.0 – Positive Affect and Well-Being. Well-being of the PWD will be assessed by caregiver proxy using the Alzheimer's Disease Related Quality of Life (ADRQL) measure. Caregiver burden will be assessed using the Dementia Caregiver Burden Scale, a validated measure created by Peipert et al. Depression will be assessed using the CES-D, the most widely used measure of depression in research, and perceived stress will be assessed using the validated and widely used Perceived Stress Scale. Activation is a domain of interest for our exploratory work. We will measure caregiver activation for self-care using the validated Patient Activation Measure. We will also measure caregiver activation for PWD's care using the validated Managing Your Loved One's Health (MYLOH) measure developed by consultant [name] and colleagues.

### **Behavioral Outcomes**

We plan to assess self-reported resource use (by the caregiver and by the care recipient by proxy) using items developed for CRx-1 and 2 to measure contacting, going to and sharing information about resources. Resource use will also be assessed using qualitative data from text messages between the community resource specialist and the caregiver. Data generated by caregivers' use of the web-based Community Resource Finder will be used to assess resource searches, selection and sharing as well as unfulfilled requests (searches that resulted in no available resources). Text message data and Community Resource Finder data will be collected via use of the NowPow system and transferred regularly to the research team.

## Health and Healthcare Outcomes

Caregiver physical health and quality of life will be assessed using the Medical Outcomes Study SF-12 and EMR data. Physical health of the PWD will be assessed by proxy using a single item global measure of physical health. Healthcare utilization will be assessed using the DEXCOM, a selfreport tool developed by Co-PI [name] and used in CRx-2.

## Sample Size

Aim 1 [primary] analyses will include ADRD caregivers who screen positive for one or more unmet HRSNs (N=172). For the primary outcome (self-efficacy for providing care at 12 months) a sample of 86 caregivers/arm allows for detection of an intervention group difference of 0.43 points (sample size calculation using a group allocation of 1:1; power=0.8;  $\alpha$ =0.05, mean=2.8 and SD=1). With this sample size, power is sufficient to see at least a half a standard deviation (SD) difference in caregiver self-efficacy between intervention and control groups; half a standard deviation is considered a minimally important difference. Assuming 25% attrition, we will still be able to detect a difference equal to half an SD. Attrition in the pragmatic CRx-2 trial was 20%; this was an even lower-intensity intervention with no ongoing resource support nor touchpoints between follow-up surveys.

## Analysis Plan

To determine the impact of CRx-D on the highest risk group, Aim 1 analyses will focus on 172 caregivers with at least 1 HRSN. Descriptive statistics will be used to summarize, overall and by study arm, sociodemographic characteristics and primary and secondary outcomes at each measured time point. The mean, standard deviation, median, and inter-quartile range will be generated for continuous variables; frequency counts and percentages will be generated for categorical variables.

The main analyses will follow the principle of intent-to-treat, and include all 172 ADRD caregivers with at least 1 unmet HRSN in the study arm to which they were allocated.

To fully leverage the longitudinal data, generalized linear mixed-effects models (GLMM) will be fit with particular interest in the time (7, 30, 90 days and 12 months post-enrollment) by study arm interaction; baseline values will be included as a covariate. Based on this model, appropriate contrasts to test the intervention effect at specific time points (e.g., 12 months) will be constructed. These contrasts will permit examination of early versus late intervention effects, valuable information for future iterations of this and other ADRD caregiver self- and family management interventions. GLMM can be used for continuous (e.g., mean caregiver self-efficacy for providing care score, patient satisfaction score, stigma score), ordinal (e.g., physical health of PWD by proxy) or binary (e.g., resource use, resource sharing) outcomes. Models will include covariates moderately associated with the outcome to remove differences attributable to baseline covariates and increase precision of the estimate of the treatment affect. Latent growth curve modeling is a viable alternative to GLMM and will be explored when sufficient variability in the distributions of patterns of outcomes by time points exist (e.g., with the binary outcomes there will be a limited number of potential patterns).

Potential moderators of the intervention effect (e.g., race, sex) will also be assessed by inclusion of a moderator by study arm interaction term. Although in the CRx-2 trial we saw no gender differences in outcomes, special consideration will be given to sex (as measured by self-reported gender) as a biological variable (moderator) and variation in intervention effects will be examined in accordance with NIH policy. In addition, based on preliminary evidence of similarity across race and ethnic groups from the CRx-2 trial, we hypothesize that the intervention effect will be similar and will

analyze for dramatic departures from this outcome (e.g., whether the intervention has no or negative effect among non-Hispanic white caregivers versus a strong positive effect among AA/B caregivers) through effect modification analyses (e.g. testing race by intervention interaction). Also, we will use mediation analyses to identify factors that mediate the relationship between the study arm and the outcome of interest. Improved understanding of moderating and mediating factors will facilitate future improvements to the intervention. For example, if the relationship between intervention effect and caregiver burden at time t is mediated by self-efficacy at time t-1, as posited in our conceptual framework, future improvements might focus the intervention's messaging more explicitly on fostering caregiver self-efficacy.

Transition models will be used to further study the impact of CRx-D on state changes in other outcomes, including unmet needs, well-being and resource use. This model will be of the general form: logit  $P(Y_{it} = 1 | Y_{it-1} = y_{it-1}) = X + y_{it-1} + y_{it-1} * X$  where X is the intervention group variable and  $Y_{it}$  is a binary outcome variable for subject i at time t. This approach will allow us to determine the frequency of transitioning into and out of a state (e.g., having any unmet HRSNs to having no unmet HRSNs) and how the intervention impacts on these transitions. This model can be extended to permit ordinal outcomes (e.g., self-efficacy for finding services to help care for the PWD). We will assume a first-order Markov model but check the sensitivity of the model to this assumption and will use robust standard errors.

We will also use survival analysis methods and methods for analyzing count data (e.g., Poisson or negative binomial regression) to explore acute and emergency healthcare utilization. For example, time from enrollment to first home EMS or ER visit will be calculated for each subject and those who never have one of these events will be censored at the end of study follow-up. Stratified Cox proportional hazards regression models will be fit with intervention group as the independent variable and clinical enrollment site as a stratification factor, due to the potential for different underlying rates based on clinical site. The proportional hazards assumption will be checked using log-log plots of survival and Schoenfeld residuals.

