An estimated 6% of all US adults today are ADRD caregivers (and the number is growing). Two thirds of ADRD caregivers are ≥ 50 years. AA/B people are twice as likely as whites to have dementia and are more likely to be home-dwelling. Approximately 40K patients who live in target region will be seen in the 3 recruitment sites during a 12 month period (~87.5K visits/year); 60% of these patients are ≥50 years and 75% are AA/B. Given the race and age composition of the target patient population, we estimate that 6-9% of patients approached for enrollment will be ADRD caregivers.

We will need to approach between 7K-10.5K patients living in the target region to recruit 364 ADRD caregivers (344 for the RCT + 20 for pretesting). This conservative assumption derives from this calculation: 10,550 patients \* 0.06 ADRD caregiver rate \* 0.71 willing to be screened (rate from CRx-2 trial) \* 0.81 cooperate (rate from CRx-2 trial). In CRx-2, we approached 3,100 UCMC patients over 8 months (387/month) to enroll 411 people into a trial with similar burden (length and number of surveys). For this study, we will need to approach 387-583 patients/month and have staffed and budgeted accordingly. To account for unforeseen challenges in recruiting, we have allotted 24 months for enrollment. If enrollment does not meet expected targets during the first quarter, we

will expand recruitment to the ER. This site sees 32-40K patients/yr from the target region and was a successful recruitment site for CRx-1 and -2. In addition, SCSS sees more than 250 PWD/yr from the target region. We can also recruit ADRD caregivers from SCSS. In two recent ADRD caregiver studies, we easily met recruitment goals at SCSS with high cooperation rates (>90%). From this group, we will recruit a caregiver advisory board using a community-engaged research approach that we created together with community members and have applied in several prior successful studies.

Preliminary data indicate that 52% of caregivers will have ≥1 unmet HRSNs. To ensure equal numbers between groups, we will use stratified randomization to allocate subjects to usual care or CRx-D by number of unmet HRSNs (0 or ≥1). Randomization will occur immediately after enrollment using the method of permuted blocks and the uniform random number function in Stata (v15). A stratum will be closed for enrollment once its accrual goal has been reached.

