The baseline survey will be administered following randomization by a trained interviewer. All caregivers will receive usual care. Participants will be blinded to the arm to which they are randomized. For caregivers randomized to the intervention arm, CRx-D will be delivered by the interviewer. Follow-up phone surveys will be conducted using computer-assisted personal interviewing (CAPI) at 7, 30, 90 days and 12 months post-enrollment. To maximize retention, a brief check-in will be conducted at 180 days and we will use text messaging and phone calls monthly between surveys to verify contact information and to schedule and remind participants about upcoming surveys. Intervention group participants can also text, email or call the CRx-D resource specialist for resource support throughout the follow-up period.

We will conduct two waves of baseline and 1 week follow-up pre-testing (Y1Q3), each with 5 ADRD caregivers with 1 or more unmet HRSNs and 5 ADRD caregivers with 0 unmet HRSNs (20 total with the two waves) to ensure survey quality and minimize risk of measurement and CAPI error. Table 1 summarizes example measures, sources and planned time points for collection. Dynamic factors will be assessed at appropriate intervals (e.g., during the last 30 days or in the interval since the last survey).

The primary outcome for Aim 1 will be assessed using the 4-item self-efficacy sub-domain from the 2015 Caregiver Dementia Care and Self-Efficacy Survey developed by Jennings et al (NIA-5P30AG028748, CMS-1C1-12-0001). We selected this relatively new measure because it is, to our knowledge, the only available measure validated specifically for ADRD caregivers that assesses self-efficacy for accessing services.

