Potential moderators of the intervention effect (e.g., race, sex) will also be assessed by inclusion of a moderator by study arm interaction term. Although in the CRx-2 trial we saw no gender differences in outcomes, special consideration will be given to sex (as measured by self-reported gender) as a biological variable (moderator) and variation in intervention effects will be examined in accordance with NIH policy. In addition, based on preliminary evidence of similarity across race and ethnic groups from the CRx-2 trial, we hypothesize that the intervention effect will be similar and will analyze for dramatic departures from this outcome (e.g., whether the intervention has no or negative effect among non-Hispanic white caregivers versus a strong positive effect among AA/B caregivers) through effect modification analyses such as testing of the race by intervention interaction. Also, we will use mediation analyses to identify factors that mediate the relationship between the study arm and the outcome of interest. Improved understanding of moderating and mediating factors will facilitate future improvements to the intervention. For example, if the relationship between intervention effect and caregiver burden at time t is mediated by self-efficacy at time t-1, as posited in our conceptual framework, future improvements might focus the intervention's messaging more explicitly on fostering caregiver self-efficacy.

Transition models will be used to further study the impact of CRx-D on state changes in other outcomes, including unmet needs, well-being and resource use. This model will be of the general

form: logit P(Yit = 1 | Yit-1 = yit-1) = X + yit-1 + yit-1\*X where X is the intervention group variable and Yit is a binary outcome variable for subject i at time t. This approach will allow us to determine the frequency of transitioning into and out of a state (e.g., having any unmet HRSNs to having no unmet HRSNs) and how the intervention impacts on these transitions. This model can be extended to permit ordinal outcomes (e.g., self-efficacy for finding services to help care for the PWD). We will assume a first-order Markov model but check the sensitivity of the model to this assumption and will use robust standard errors.

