### Handling of Missing Data

We aim to minimize missing data by employing interviewer-administered surveys and communicating to participants the protections of a Certificate of Confidentiality. Using these strategies, item non-response ranged from 0-3% in the CRx-2 trial. To avoid potential bias due to missing data, analyses will be conducted using multiple imputation with the chained equations method or inverse probability weighting to account for dropout and/or item non-response. In addition, characteristics of caregivers who complete each follow-up survey will be compared to caregivers who do not. We will follow all caregivers through 12 months even if they no longer care for the PWD.

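### The secondary transition model shows no survey-interval term although surveys are 7, 23, 60 and about 275 days apart, so its transition frequencies have no time unit and cannot be compared across strata.

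*SAP*

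**What the plan says.** The transition model appears in the Overall Statistical Analysis Plan (Aim 1 analysis) and again in the Aim 1 SAP, Analysis Plan. It is presented as a general form: the logit of being in a state depends on arm, the previous state and their product, "where X is the intervention group variable and Yit is a binary outcome variable for subject i at time t". The stated purpose is: "This approach will allow us to determine the frequency of transitioning into and out of a state". On assumptions, the plan says: "We will assume a first-order Markov model but check the sensitivity of the model to this assumption".

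Follow-up surveys are "at 7, 30, 90 days and 12 months post-enrollment". The mixed model in the same Analysis Plan does carry time, through the "time (7, 30, 90 days and 12 months post-enrollment) by study arm interaction". That term does not appear in the transition model.

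The Aim 2 strategy in the overall plan reuses the approach for caregivers without unmet needs at baseline. The detailed Aim 2 SAP does not repeat the model, but keeps the incidence of unmet needs in that group as a target. Dropout is to be handled by "multiple imputation with the chained equations method or inverse probability weighting to account for dropout and/or item non-response" (Aim 1 SAP, Handling of Missing Data).

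**The concern.** A step from baseline to day 7 and a step from day 90 to month 12 are different lengths of exposure to change. Without an interval term they share one transition probability per prior state and arm. The result depends on how the surveys happen to be spaced and on which steps each prior state can be observed in. In a stratum where everyone starts without a need, losses can be seen only from the second step on, and mostly in the last and longest one, while gains are counted from the first week.

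What is at stake is the secondary result on how often caregivers enter and leave unmet need, and how the intervention changes that. The pooled figure could not be restated per month. Entry could not be set against exit, nor one baseline stratum against the other, and a real arm effect would look smaller than it is at any single step.

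**Working it through.** The SAP states no figure for this model, so there is none to reproduce.

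**Inputs**
- Survey times from the SAP: 7, 30, 90 days and 12 months (taken as 365 days). Steps: 7, 30 − 7 = 23, 90 − 30 = 60, 365 − 90 = 275 days.
- Prevalence from the overall plan: "Preliminary data indicate that 52% of caregivers will have" at least one unmet need.
- Transition rates: the documents give none. Assumed gain λ = 0.78 and loss μ = 0.72 per year, so that λ/(λ+μ) = 0.78/1.50 = 0.52. Range: both halved to both doubled.
- 12-month completion of 75%, from the Aim 1 SAP, Sample Size: "Assuming 25% attrition, we will still be able to detect a difference equal to half an SD".
- Need is treated as a point-in-time state.

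**Formulas** (t in years)
- P(gain) = λ/(λ+μ) × (1 − exp(−(λ+μ)t))
- P(loss) = μ/(λ+μ) × (1 − exp(−(λ+μ)t))
- Pooled value = expected transitions / expected person-steps at risk. The printed form has one free value per combination of arm and prior state, so this ratio is what it returns.

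**All start without need, full completion (per caregiver)**

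| Step (days) | Share without need | Share with need | P(gain) | P(loss) | Gains | Losses |
|---|---|---|---|---|---|---|
| 7 | 1.0000 | 0.0000 | 0.0147 | 0.0136 | 0.0147 | 0.0000 |
| 23 | 0.9853 | 0.0147 | 0.0469 | 0.0433 | 0.0462 | 0.0006 |
| 60 | 0.9397 | 0.0603 | 0.1136 | 0.1049 | 0.1068 | 0.0063 |
| 275 | 0.8392 | 0.1608 | 0.3520 | 0.3250 | 0.2954 | 0.0522 |
| Sum (unrounded) | 3.7642 | 0.2358 | | | 0.4632 | 0.0592 |

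- Pooled gain: 0.4632/3.7642 = 12.3%. Rates halved to doubled: 7.6% to 17.7%.
- Pooled loss: 0.0592/0.2358 = 25.1%.
- The last step supplies 0.2954/0.4632 = 64% of the gains.

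**All start with need.** Losses 0.0136 + 0.0427 + 0.0991 + 0.2767 = 0.4321 over 3.7823 person-steps in need: pooled loss 11.4%. The same loss rate of 0.72 per year therefore reads as 11.4% or 25.1%, depending only on the baseline stratum.

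**Time unit.** The 30-day gain is 0.52 × (1 − exp(−1.5 × 30/365)) = 6.0%. Over the mean step of 365/4 = 91.25 days it is 16.3%. The pooled 12.3% is neither, so dividing by the mean gap does not rescue it.

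**Arm effect, all starting without need.** With a gain-rate ratio of 0.6, the intervention gain rate is 0.6 × 0.78 = 0.468 per year. The pooled gain is 8.15%, against 12.31% in controls. Pooled odds ratio: (0.0815/0.9185)/(0.1231/0.8769) = 0.63. Step-specific gains are 0.0089, 0.0284, 0.0699 and 0.2330, giving odds ratios of 0.60, 0.59, 0.59 and 0.56. All four lie further from 1. With no effect and equal completion, both arms have the same mixture and the odds ratio is 1.00.

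**Day 7 not collected** (steps 30, 60, 275). (0.0603 + 0.1068 + 0.2954)/(1 + 0.9397 + 0.8392) = 0.4625/2.7789 = 16.6%.

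**Observed pairs only, 75% seen at 12 months.** (0.4632 − 0.25 × 0.2954)/(3.7642 − 0.25 × 0.8392) = 0.3893/3.5544 = 11.0%.

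**The case against.** *The formula is schematic.* It shows no intercept, coefficients or covariates and is called a general form. A reader might infer that the plan excludes time; it does not say so. This stands: the interval term is unspecified, not ruled out. But an analyst who fits what is printed gets the pooled result.

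*The frequency depends on 12-month retention.* A reader might infer this, and it would hold for observed pairs (12.3% to 11.0%). The SAP, however, plans imputation or weighting for dropout. If that is applied to this model, the shift disappears in expectation. It does not supply a time unit or undo the pooling.

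*Nothing else in the plan gives dated transitions.* That would be too strong. Within one baseline stratum everyone shares a starting state, so the planned percentage at each survey is itself a baseline-to-survey transition probability. In the chain above, 40.4% of those starting without need are in need at 12 months, which is the 365-day gain probability. What those summaries leave out is moves between surveys and relapse.

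*The first-order check would fail because of the spacing.* The plan names no test, and within a single baseline stratum, which is how it studies unmet need, the effect is negligible.

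*Day 7 may not apply to every outcome.* Collection times are in a Table 1 that the text supplied does not contain. Without day 7 the size changes and the problem stays.

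*The data are not point-in-time states.* True: after week 1 the needs survey asks about the period since the last interview (Aim 1 SAP, Psychosocial Outcomes). The percentages above are therefore illustrative for unmet need. The lengthening look-back adds to the difficulty.

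**Conclusion.** The point holds for this secondary model, at low priority. Fitted as printed, it yields a per-survey mixture with no time unit. Its entry and exit figures are not comparable with each other or across strata (loss 11.4% against 25.1% from one process), and it pulls a true effect toward 1 (0.63 against 0.56 to 0.60). The sizes rest on assumed constant rates matched to 52% prevalence, point-in-time states, and collection at day 7. The lack of a time unit follows from the spacing alone. The null arm comparison with equal completion is not distorted. The primary analyses of both aims do not use this model and are unaffected.

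**What to change.** Write the model as logit P = α_k + γ_k·y(t−1) + β·X + δ·y(t−1)·X, with k the survey interval. Within one baseline stratum, omit γ_1: everyone has the same prior state at the first step, so it cannot be identified.

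Alternatively, fit a two-state continuous-time Markov model on actual days between surveys. This is preferable where first-week transitions are few: at the assumed rates, 172 × 0.0147 = about 2.5 of the 172 caregivers without baseline need would gain one by day 7.

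In either case:
- report transitions per interval or per fixed period such as 30 days;
- run the first-order check inside that model;
- state that the missing-data section applies to it;
- state which surveys collect each outcome;
- define the follow-up need state by the past-30-day item where available, so that the look-back does not grow with the gap. At day 30 this window still overlaps the day-7 survey, which should be noted.

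Cost: a few model terms and a few sentences in the SAP. No new data.
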